### 8.5.3 Analysis of Secondary and Safety Endpoints

#### 8.5.3.1 Analysis of Safety Endpoints

The extent of exposure to avelumab will be characterized by duration (weeks), number of administrations, cumulative dose (mg/kg), dose intensity (mg/kg/week), relative dose intensity (actual dose given/planned dose), number of dose reductions, and number of dose delays.

Safety analyses will be performed on the Safety Analysis Set. The safety endpoints will be tabulated by dose level and cohort, using descriptive statistics.

Safety assessments will be based on review of the incidence of AEs, ADRs, and changes in vital signs, ECGs, body weight, and laboratory values (hematology and serum chemistry).

The on treatment period is defined as the time from the first administration of avelumab to the last administration of avelumab date plus 30 days or the earliest date of subsequent anticancer drug therapy minus 1 day, whichever occurs first.

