#### Adverse Events

All AEs will be coded according to the Medical Dictionary for Regulatory Activities. Severity of AEs will be graded using the NCI-CTCAE v4.03 toxicity grading scale.

Treatment-emergent AEs are those events with an onset date occurring during the on-treatment period or if the worsening of an event is during the on-treatment period.

The incidence of TEAEs, regardless of attribution and AEs, defined as possibly related to study treatment will be summarized by Preferred Term and System Organ Class, and described in terms of intensity and relationship to study treatment. Adverse events (serious and nonserious) will be considered TEAEs, except for AEs which started prior to the first administration of avelumab (unless a worsening of the event is recorded after the first administration of avelumab, in which case the event will be considered a TEAE). All premature terminations will be summarized by the primary reason for study withdrawal.

Descriptive statistics will be examined for indications of dose-related ADRs.

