Draft 0.3	11MAY2018	PPD	Modified per sponsor's comments received on 26MAR2018 and 10MAY2018.
Draft 0.4	29MAY2018	PPD	Modified per sponsor's comments received on 21MAY2018 and 24MAY2018.
Final 1.0	01JUN2018	PPD	Modified per sponsor's comments received on 25MAY2018 and 31MAY2018.
Final 2.0	13AUG2019	PPD	
 1. Add appendix of irAE and IRR 2. Add appendix of Toxicities for Laboratory Evaluations 3. Modify Section 12.2 Medications 4. Clarify ADA in secondary endpoint. 5. Add rule for incomplete date of prior/concomitant medication. 6. Modify definition of re-initiation

4 Purpose of the Integrated Analysis Plan

The purpose of this IAP is to document technical and detailed specifications for the final analysis of data collected for protocol MS100070-0035.

Results of the analyses described in this IAP will be included in the Clinical Study Report (CSR). Additionally, the planned analyses identified in this IAP will be included in regulatory submissions or future manuscripts. Any post-hoc, or unplanned analyses performed to provide results for inclusion in the CSR but not identified in this prospective IAP will be clearly identified in the CSR.

The IAP is based upon section 8 (Statistics) of the trial protocol and protocol amendments and is prepared in compliance with ICH E9.

5 Objectives and Endpoints

	Objective	Endpoint	IAP section
Primary Objective	
 • To evaluate the maximum tolerated dose (MTD) of avelumab (MSB0010718C) monotherapy in Chinese subjects. • To characterize the pharmacokinetics (PK) of avelumab in Chinese subjects. 	
Primary Endpoint
 
 • Occurrence of DLTs during the DLT observation period (first 21 days of treatment; excluding 10 mg/kg once weekly cohort). • PK profiles in Chinese subjects. 	
15
 
16.1
 
16.2

Secondary Objective	
 To determine the safety and tolerability of avelumab by assessing treatment-emergent adverse events (TEAEs) and treatment-related AEs for all dose groups according to the NCI-Common Terminology Criteria for Adverse Events (CTCAE) v4.03. To characterize immunogenicity of avelumab in Chinese subjects. 	Secondary Endpoint 
 Occurrence of TEAEs for all dose groups according to NCI-CTCAE v4.03. Occurrence of treatment-related AEs for all dose groups according to NCI-CTCAE v4.03. Serum titers of ADA against avelumab. 	14 15

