6.3 Final Analysis

The final analysis of study data will be conducted after End of Study, which is defined as the last patient complete 90-day safety follow-up phone call or last patient died, whichever comes first.

Additional data from primary analysis up to this cut-off date will be analyzed and presented as an addendum of CSR.

7 **Changes to the Planned Analyses in the Clinical Trial Protocol**

Biomarker related analysis are not planned in this IAP because biomarker testing will be done at a later time.

8 **Protocol Deviations and Analysis Sets**

8.1 **Definition of Protocol Deviations**

Important protocol deviations are protocol deviations that might significantly affect the completeness, accuracy, and/or reliability of the study data or that might significantly affect a subject's rights, safety, or well-being.

Important protocol deviations include:

- Subjects that receive study medication despite not satisfying the inclusion criteria or violating exclusion criteria;
- Subjects that develop withdrawal criteria whilst on the study but are not withdrawn;
- Subjects that receive the wrong treatment or an incorrect dose;
- Subjects that receive an excluded concomitant medication.

The following important deviations will be identified and confirmed prior to or at the Data Review Meeting:

- Deviations from the inclusion and exclusion criteria;
- Deviations post inclusion.

Important protocol deviations are specified in Appendix 18.1, and will be summarized in a table and presented in a data listing. All-important protocol deviations should be documented in SDTM datasets in which identified through sites monitoring, medical review or programming.

8.2 **Definition of Analysis Sets**

Screening Analysis Set (SCR): all subjects who signed the ICF(s).

DLT Analysis Set (DLT): all subjects with data used for implementing the dose-escalation schedule (excluding 6 subjects in 10 mg/kg once weekly cohort). These subjects should have received all avelumab administrations in the DLT observation period (first 21 days of treatment) or should have stopped treatment because of DLTs in the DLT observation period.

Safety Analysis Set (SAF): all subjects who have received at least 1 dose of avelumab. The Safety Analysis Set will be used for all analyses of safety and efficacy.

Efficacy Population: all subjects who have received at least 1 dose of avelumab and have measurable disease at baseline according to Investigator assessment.

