15.2 Adverse Events (AE)

An AE is any untoward medical occurrence in a subject or clinical investigation subject administered a pharmaceutical product, which does not necessarily have a causal relationship with this treatment. An AE can therefore be any unfavorable and unintended sign (including an abnormal laboratory finding), symptom, or disease temporally associated with the use of a medicinal product, whether or not considered related to the medicinal product.

If the severity/intensity of a particular AE is not specifically graded by the guidance document, the Investigator is instructed to revert to the general definitions of Grade 1 through Grade 5 and use his or her best medical judgment.

The 5 general grades are:

- Grade 1: Mild
- Grade 2: Moderate
- Grade 3: Severe
- Grade 4: Life-threatening or disabling
- Grade 5: Death related to AE

AEs will be coded using the latest version of Medical Dictionary for Regulatory Activities (MedDRA). The severity of AEs will be graded by the investigator using the NCI-CTCAE version 4.03.

Treatment emergent adverse events (TEAEs) are those events that emerge during treatment having been absent pre-treatment, or worsen relative to the pre-treatment state and with onset dates

occurring within the first dosing day of study dose levels until 30 days after the last dose of study treatment.

All analyses described **Error! Reference source not found.** will be based on TEAEs (started during the on-treatment period) if not otherwise specified. The AE listings will include all AEs (whether treatment-emergent or not). AEs outside the on-treatment period will be flagged in the listings. A separate listing including AEs started after the on-treatment period will also be provided.

- **Related Adverse Events:** adverse events with relationship to study treatment (as recorded on the AE eCRF page, Relationship with study treatment = Related) reported by the investigator and those of unknown relationship (i.e. no answer to the question “Relationship with study treatment”).
- **Serious Adverse Events (SAE):** serious adverse events (as recorded on the AE eCRF page, Serious Adverse Event = Yes).
- **Related SAEs**
- **Adverse Events Leading to Treatment Discontinuation:** adverse events leading to permanent discontinuation of study treatment (as recorded on the AE eCRF page, Action taken with study treatment = Drug withdrawn).
- **Related AE Leading to Treatment Discontinuation**

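### SAP 15.2 counts TEAEs to last dose + 30 days without the protocol's cut at the next anticancer drug, and its visible text never defines the on-treatment period

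*SAP*

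**What the plan says.** **Protocol 8.5.3.1.** The on-treatment period runs from the first avelumab administration to the last administration plus 30 days, "or the earliest date of subsequent anticancer drug therapy minus 1 day, whichever occurs first". The Adverse Events part of that section ties the endpoint to the period: "Treatment-emergent AEs are those events with an onset date occurring during the on-treatment period", or events that worsen during it. A later sentence there says that serious and nonserious AEs "will be considered TEAEs, except for AEs which started prior to the first administration of avelumab", unless they worsen afterwards. That sentence gives no end date.

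**SAP 15.2.** TEAEs have onset dates "occurring within the first dosing day of study dose levels until 30 days after the last dose of study treatment". Subsequent therapy is not mentioned. The SAP then says that the analyses "will be based on TEAEs (started during the on-treatment period) if not otherwise specified", and that "AEs outside the on-treatment period will be flagged in the listings". The same term governs the SAE listing flag in 15.2.4 and the worst laboratory grade in 15.3. The ECG and ECOG shift tables in 15.5 use the worst on-treatment result. No visible part of the SAP defines the term, including the abbreviations, section 9.3 and the opening of section 15.

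**SAP sections 4 and 7.** Section 4 states: "The IAP is based upon section 8 (Statistics) of the trial protocol". The only change from the protocol that section 7 declares is: "Biomarker related analysis are not planned in this IAP because biomarker testing will be done at a later time".

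**The concern.** Occurrence of TEAEs is a secondary endpoint. The protocol's cut keeps events that begin after a subject has moved to another anticancer drug out of the avelumab count. The SAP's stated rule has no cut, so it attributes those events to the avelumab treatment period, and nothing in the SAP shows that this was a decision.

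The gap can hold data. Protocol 7.4.1.3 collects all AEs through the 30-day Safety Follow-up Visit. Table 1-1 records further anticancer therapy during follow-up, and its footnotes provide for another anticancer therapy starting within the 7 days allowed for the End-of-Treatment Visit. Cohorts have 3 or 6 subjects, so one subject can visibly change a percentage.

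**Working it through.** The plan gives no figure to reproduce. The check compares the two windows and then sizes the difference.

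**Inputs**
- Last avelumab dose = day 0.
- SAP 15.2: the TEAE window ends on day 30.
- Protocol 8.5.3.1: the window ends on the earlier of day 30 and the day before the next anticancer drug.
- d = day on which the next anticancer drug starts. This is an assumption, because the documents give no timing.
- Cohort sizes from Protocol 5.1.1.1 and 5.1.2.1.2: 3 subjects in the first cohort if there is no DLT, otherwise 6; 6 in the others. The Synopsis plans about 21 subjects, up to about 24.

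**Window difference**

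Protocol end day = min(30, d - 1). Excess of the SAP window = 30 - min(30, d - 1) = max(0, 31 - d).

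| d (assumed) | Protocol end day | SAP end day | Excess days |
|---|---|---|---|
| 7 | 6 | 30 | 24 |
| 14 | 13 | 30 | 17 |
| 21 | 20 | 30 | 10 |
| 28 | 27 | 30 | 3 |
| 31 or later, or none | 30 | 30 | 0 |

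**Effect on a table row**

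A row changes only if a subject's sole qualifying event for that row starts in the gap. One such subject moves it by:
- 1/3 = 33.3 percentage points in a cohort of 3
- 1/6 = 16.7 points in a cohort of 6
- 1/21 = 4.8 or 1/24 = 4.2 points overall

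The row for any TEAE will move less often, because most subjects may already have an event. Rows for Grade 3 or higher events, serious events and single preferred terms are more exposed. Treatment-related rows are less exposed because they also need the investigator's attribution.

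**Direction**

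At the end of the window, the SAP's end day is never earlier than that of the on-treatment period in Protocol 8.5.3.1. The SAP rule can therefore only add events relative to it.

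**Readings of the undefined term**
- If it means the SAP's own 30-day window, SAP 15.2 is consistent with itself and differs from the protocol by the days above.
- If it imports the protocol's definition, the sentence limiting the analyses removes events that the preceding SAP sentence has just called TEAEs.

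The first reading is the more natural, because the explicit window comes immediately before.

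**The case against.** **The protocol is not a single clean standard.** Its later TEAE sentence has no end date and no cut, so the SAP window lies between two protocol statements. This stands, and it means that the protocol sentence must be reconciled too. It does not remove the mismatch: the protocol defines the on-treatment period explicitly, with the cut, and defines TEAEs by it.

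**The impact is small and traceable.** The analyses are descriptive, and the SAP lists all AEs and post-treatment anticancer therapy. If those listings carry start dates, each affected case can be found by hand. Every value of d is assumed, and the 24-day excess needs a new drug on day 7, before the next two-weekly dose would be due. All of this stands and limits the size of the point. It does not correct the tabulated counts, and the listing flags rest on the same undefined term.

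**A definition may exist out of sight.** SAP section 14 is redacted, so this cannot be excluded.

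Three stronger readings are tempting, but the documents do not support them:
- *The SAP contradicts itself beyond repair.* It does so only if the term imports the protocol's definition, and that is the less natural reading.
- *The 90-day onset limit for immune-related events in SAP Appendix 18.2 conflicts with the TEAE window.* The appendix is a case definition for flagging events, while 15.2.1 and 15.2.5 tabulate treatment-emergent ones. Requiring both conditions is the natural reading.
- *The SAP rule hides toxicity.* At this boundary it can only add events relative to the on-treatment period in Protocol 8.5.3.1.

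**Conclusion.** The point holds as an undeclared difference between SAP and protocol, together with a term that the visible SAP uses but does not define. As written, SAP 15.2 counts AEs that begin after another anticancer drug, up to day 30, as avelumab TEAEs; Protocol 8.5.3.1 ends the on-treatment period before them.

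The excess depends on the assumed d and is zero from day 31. The row shifts also assume a subject whose only qualifying event starts in the gap. How often that happens cannot be estimated from the documents. The effect is confined to descriptive secondary safety tables, listing flags and on-treatment summaries; DLT and PK results are unaffected. The wording should be settled before the tables are programmed.

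Confidence is high that the two windows differ. It is lower that the SAP nowhere defines the term, because of the redaction.

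**What to change.** 1. In SAP 15.2, define the on-treatment period once, as in Protocol 8.5.3.1: first dose to the earlier of last dose + 30 days and the start of subsequent anticancer drug therapy minus 1 day. Define a TEAE as onset or worsening within it, and refer 15.2.4, 15.3 and 15.5 to that definition.
2. If last dose + 30 days alone is intended, declare it in SAP section 7 as a departure, with the reason, and define the on-treatment period to match.
3. Reconcile the later TEAE sentence in Protocol 8.5.3.1, which has no end date, with the on-treatment definition.
4. State which last dose closes the period for subjects who re-initiate avelumab under SAP 13.3. Neither document's window says so.

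The cost is SAP wording and one derived end date per subject. SAP 12.3 shows that anticancer drug therapy after discontinuation is already collected on the eCRF. That the page holds a start date is an assumption, but the protocol's own definition cannot be applied without one. No additional assessment of subjects is needed.

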15.2.2 Adverse Events Leading to Treatment Discontinuation

The frequency (number and percentage) of patients with each of the following will be presented for TEAEs leading to permanent discontinuation of avelumab, by treatment dose group:

- AEs leading to discontinuation of avelumab by SOC and PT
- Related AEs leading to discontinuation of avelumab by SOC and PT

15.2.3 The listing of all AEs leading to avelumab discontinuation will also be provided Deaths

The frequency (number and percentage) of patients who died during the trial period and who died within 30 days after last dose or 60 days after first dose of avelumab as well as the primary reason for death, will be tabulated based on information from the “DEATH” and “SUBJECT STATUS / SURVIVAL FOLLOW-UP” eCRF page.

The following summaries will be provided:

- All deaths
- Number of deaths within 30 days after last dose of study treatment
- Number of deaths within 60 days after first dose of study treatment
- Primary Reason of death
 - Progressive disease and/or disease related condition
 - Event unrelated to avelumab
 - Event related to avelumab
 - Event related to Physician's Choice
 - Unknown

In addition, date and cause of death will be provided in an individual subject data listing together with selected dosing information (study treatment received, date of first / last administration, number of infusions received for treatment, day relative to first infusion and day relative to most recent infusion) and will include the following information:

- AEs with fatal outcome (list preferred terms of AEs with outcome = Fatal, as well as AEs of Grade 5)
- Flag for death within 30 days of last trial drug treatment
- Flag for death within 60 days of first trial drug treatment

15.2.4 Serious Adverse Events

The following summary tables will be provided for serious TEAEs detailing the number and percentage of subjects by MedDRA primary SOC (ordered alphabetically) and PT (ordered alphabetically); each subject will be counted only once within each PT or SOC:

- SAEs by SOC and PT
- Related SAEs by SOC and PT

The listings of all SAEs will also be provided including a flag for SAEs with onset outside of the on-treatment period.

15.2.5 Adverse Events of Special Interest

Any AE that is suspected to be a potential irAE and infusion related reactions will be considered an adverse event of special interest (AESI). The frequency (number and percentage) of patients with each of the following will be presented for treatment emergent irAEs, by dose level/cohort:

- Any irAEs

- Any related irAEs
- Any serious irAEs
- Any related serious irAEs
- Any irAEs by NCI-CTCAE severity grade (≥ 3 , ≥ 4)
- Trial treatment related irAEs by NCI-CTCAE severity grade (≥ 3 , ≥ 4)
- Any irAEs leading to treatment discontinuation
- Any related irAEs leading to treatment discontinuation
- Any irAEs leading to death
- Any related irAEs leading to death

The frequency (number and percentage) of patients with each of the following will be presented for treatment emergent IRRs, by treatment cohort:

- Any IRRs
- Any related IRRs
- Any serious IRRs
- Any related serious IRRs
- Any IRRs by NCI-CTCAE severity grade (≥ 3 , ≥ 4)
- Trial treatment related IRRs by NCI-CTCAE severity grade (≥ 3 , ≥ 4)
- Any IRRs leading to treatment discontinuation
- Any related IRRs leading to treatment discontinuation
- Any IRRs leading to death
- Any related IRRs leading to death

15.3 Clinical Laboratory Evaluation

All laboratory assessments are performed at local laboratories and comply with local requirements.

Laboratory values (including corresponding normal ranges) from local laboratories will be converted into the standard units by data management. The results in standard units will be used for the analyses.

Laboratory results will be classified according to the NCI-CTCAE toxicity grading version 4.03. If toxicities for high and low values of a specific parameter are defined, these toxicities will be analyzed separately for the parameter as “Parameter low” and “Parameter high” (appendix 18.3).

Laboratory results that are not part of the NCI-CTCAE will be presented according to the categories: below normal limits, within normal limits and above normal limits (according to the local laboratories normal ranges).

- **Hematology:** Hematocrit, Hemoglobin, Platelet count, Red blood cells (RBC) count, White Blood Cell Count, Absolute lymphocytes count, Lymphocytes, Absolute Neutrophils count, Neutrophils, Absolute monocyte count, Monocytes, Absolute eosinophil count, Eosinophils, Absolute basophil count, Basophils, RBC morphology, Absolute reticulocytes count, Reticulocytes, Mean corpuscular hemoglobin (MCH), Mean corpuscular volume (MCV), Mean corpuscular hemoglobin concentration (MCHC).
- **Hemostaseology:** Activated partial thromboplastin time (aPTT), Prothrombin time (PT), International Normalized Ratio (INR).
- **Biochemistry:** Albumin, Alkaline phosphatase, Alanine Aminotransferase (ALT), Amylase, Aspartate Aminotransferase (AST), Gamma Glutamyl Transpeptidase (GGT), Blood Urea Nitrogen (BUN), Urea, Calcium, Chloride, Cholesterol, Creatine kinase, Creatinine, C-Reactive Protein (CRP), Glucose, Lactate dehydrogenase (LDH), Lipase, Phosphorus, Magnesium, Potassium, Sodium, Total bilirubin, Protein total, Uric acid, Triglycerides, Hemoglobin A1c.
- **Hormonal tests:** Free Thyroxine (T4), Thyroid-Stimulating Hormone (TSH), Follicle-stimulating hormone.
- **Urinalysis:** pH, Specific gravity, Protein content, Sediment analysis, Albumin, Immunoglobulin G.

NCI-CTCAE grades available:

The laboratory toxicities will be tabulated by the worst on-treatment CTCAE grade or the shift of CTCAE grade from baseline to worst grade during on-treatment period using descriptive statistics (count and percentage). The highest CTCAE grade during the on-treatment period is considered as the worst grade for the summary.

- The worst grade during the on-treatment period will be summarized considering only patients with post baseline laboratory samples: Laboratory tests by NCI-CTCAE grade (0, 1, 2, 3, 4, and missing).

The shift table will summarize baseline CTCAE grade vs. the worst on-treatment CTCAE grade (grade = 0, 1, 2, 3, 4, missing). The above analyses apply to the following hematology and biochemistry parameters which can be graded per NCI-CTCAE:

- Hematology: Hemoglobin, Lymphocytes, Neutrophils, Platelets, White Blood Cell.

- Biochemistry: Creatinine, Alanine Aminotransferase, Aspartate Aminotransferase, Gamma Glutamyl Transferase, Total Bilirubin, Lipase, Amylase, Albumin, Alkaline Phosphatase, Glucose, Uric Acid, Sodium, Potassium, Calcium, Magnesium, Cholesterol, Creatine kinase, Triglyceride, Phosphorus.

Tables will summarize, separately for hematology and biochemistry parameters, the shift from baseline grade to worst on-treatment grade by parameters and dose level.

NCI-CTCAE grades not available:

The worst on-treatment value for hematology and biochemistry parameters which cannot be graded per NCI-CTCAE will be summarized by parameter according to the local laboratories normal ranges as follows:

- Shift from baseline value (low, normal, high) to above normal during on-treatment period
- Shift from baseline value (low, normal, high) to below normal during on-treatment period.

The above analyses apply to the following hematology and biochemistry parameters which cannot be graded per NCI-CTCAE:

- Hematology: Hematocrit, Red Blood Cells, RBC morphology, Monocytes, Eosinophils, Basophils, Reticulocytes, MCH, MCV, MCHC.
- Biochemistry: Total Protein, Blood Urea Nitrogen, Blood Urea, Chloride, C-Reactive Protein (CRP), Glucose, Lactate dehydrogenase, Hemoglobin A1c.

Quantitative data will also be examined for trends using descriptive statistics (n, missing, mean, SD, median, Q1, Q3, minimum, and maximum) of actual values, absolute changes and percent changes from baseline to each visit over time. This summarization will apply to hematology and chemistry parameters with numeric results assessed at baseline, post-baseline, discontinuation, end of treatment, and safety follow-up visits.

Listing of clinically significant hematology values and listing of clinically significant biochemistry values will also be provided. Clinically significant values are defined as values with associated NCI-CTCAE grade greater or equal to 3. The following information will be included in those listings:

- Selected dosing information: date of first/last administration
- Laboratory parameter with unit
- Visit of laboratory parameter measurement
- Collection date of laboratory parameter
- Value of laboratory parameter
- Local laboratories normal ranges for laboratory parameter (lower limit of normal and upper limit of normal)

- Normal range indicator for value of the laboratory parameter (Low, Normal, High)
- Associated grade for value of the laboratory parameter according to NCI-CTCAE if applicable.

Other laboratory parameters

The following laboratory parameters collected in the CRF will be presented in specific listing presenting all collected data-fields in the CRF.

- Hemostaseology: Activated partial thromboplastin time (aPTT), Prothrombin time (PT), International Normalized Ratio (INR)
- Hormone: Free T4 and TSH
- Urinalysis: all urinalysis parameters
- Pregnancy test
- Serology

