21. Subjects will be followed every 12 weeks ( $\pm 7$  days) for survival (including assessment of any further anticancer therapy).

**Table 1-3 Schedule of Assessments – Pharmacokinetic and Antidrug Antibody Sampling for Subjects Receiving Avelumab Once Every 2 Weeks**

Assessment	Treatment Phase													EOT Visit	Safety Follow-up	
	V1					V2		V3		V4		V7		Until Progression	Within 7 days after decision to discontinue IMP	30 days (± 5 days) after last IMP
	W1 D1		W1 D2	W1 D3	W2 D8	W3 D15		W5 D29		W7 D43		W13 D85				
	Prior to infusion	End of infusion				Prior to infusion	End of infusion									
PK sampling 	X	X	X	X	X	X	X	X	X	X	X	X	X	6-weekly up to W25 (D169), then 12-weekly	X	X
ADA sampling 	X					X		X		X		X		6-weekly up to W25 (D169), then 12 weekly to EOT		X

ADA: antidrug antibody; D: Day; EOT: End-of-Treatment; IMP: investigational medicinal product; PK: pharmacokinetics; V: Visit; W: Week.

1. For subjects receiving avelumab once every 2 weeks, PK serum samples will be collected at the following time points:

- Day 1: within 2 hours prior to and at the end of the 1-hour infusion, and at 0.5, 1, 2, 4, 6, and 12 hours after the end of the infusion.
- Day 2: 2 samples will be collected 24 and 36 hours after the end of the infusion.
- Day 3: a single sample will be collected 48 hours after the end of the infusion.
- Day 8: a single sample will be collected 168 hours after the end of the infusion.
- Days 15, 29, 43, 85, 127, and 169 (Week 25): samples will be collected within 2 hours prior to infusion (trough value) and immediately after the infusion is completed (peak value).
- Every 12 weeks beyond Week 25: a single sample will be collected within 2 hours prior to infusion (trough value).
- EOT Visit.
- 30-day Safety Follow-up Visit.

\*The time window for PK sampling time points are: + 10 minutes for the end of infusion sample collection on Day 1;  $\pm$  10 minutes for 0.5 and 1 hour after the end of infusion;  $\pm$  20 minutes for 2, 4, and 6 hours after the end of infusion;  $\pm$  2 hours for 12, 24, 36, 48, and 168 hours after the end of infusion. The time window for PK sampling time points is applicable for all scheduled PK sample collection for all subjects.

2. For subjects receiving avelumab once every 2 weeks, ADA serum samples will be collected at the following time points:

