### 7.1.4.1 30-day Safety Follow-up Visit

All subjects will have a Safety Follow-up Visit scheduled 30 days ( $\pm 5$  days) after the last administration of avelumab.

After the EOT Visit, all AEs have to be documented until the 30-day Safety Follow-up Visit. After this visit, all SAEs and all treatment-related nonserious AEs must be documented until the 90-day Safety Follow-up Phone Call. Subjects with an ongoing SAE at the 30-day Safety Follow-up Visit

must be monitored and followed up by the Investigator until stabilization or until the outcome is known.

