## Laboratory Variables

Laboratory results will be classified by grade according to NCI-CTCAE v4.03. The worst on study grades after the first administration of avelumab will be summarized. Shifts in toxicity grading from first treatment to highest grade will be displayed. Results for variables that are not part of NCI-CTCAE will be presented as below, within, or above normal limits. Only subjects with postbaseline laboratory values will be included in these analyses.

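### The worst-grade and ECOG-shift tables and the TEAE window close at last dose + 30 days, but the last safety visit may fall on Days 25-35, so late visits drop out of the tables and early visits leave an AE collection gap

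*SAP*

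**What the plan says.** **Analysis window.** For graded laboratory parameters, SAP 15.3 says: "The highest CTCAE grade during the on-treatment period is considered as the worst grade for the summary". It applies the same on-treatment limit to the grade-shift tables and to the normal-range shifts for parameters without CTCAE grades. SAP 15.5.2 tabulates ECOG from baseline to the worst on-treatment status. The readable SAP does not define the on-treatment period separately. Protocol 8.5.3.1 runs it from first dose "to the last administration of avelumab date plus 30 days or the earliest date of subsequent anticancer drug therapy minus 1 day", whichever comes first.

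**TEAE window.** Protocol 8.5.3.1 ties TEAEs to that period: "Treatment-emergent AEs are those events with an onset date occurring during the on-treatment period", or worsening in it. SAP 15.2 uses onset "occurring within the first dosing day of study dose levels until 30 days after the last dose of study treatment", without the cut at new anticancer therapy.

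**Visit window.** Protocol Table 1-1 places the Safety Follow-up Visit at "30 days (± 5 days) after last IMP". It schedules hematology, core chemistry, vital signs and ECOG there.

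**AE collection.** All AEs are documented up to that visit. Protocol 7.1.4.1 then narrows the collection: "After this visit, all SAEs and all treatment-related nonserious AEs must be documented until the 90-day Safety Follow-up Phone Call".

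**Protocol rule for laboratory grades.** Protocol 8.5.3.1, under Laboratory Variables, says: "The worst on study grades after the first administration of avelumab will be summarized". SAP Section 7, which records changes from the protocol, mentions only the biomarker analyses.

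**The concern.** The analysis windows close on a fixed day, while the visit that feeds them may fall up to 5 days either side of it. A subject seen within the permitted window can still have that visit's laboratory and ECOG results left out of the worst-value tables. A subject seen early has full AE collection stopped while the TEAE window is still open. In both cases what is tabulated depends partly on the calendar day of a compliant visit.

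Cohorts have 3 or 6 subjects, so one omitted value can move a cohort's percentage noticeably. Occurrence of TEAEs, whatever their attribution, is a secondary endpoint. The laboratory rule also differs from the protocol's own, and the SAP does not say so.

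**Working it through.** The plan gives no figure to reproduce here. The check is day arithmetic, with the day of last dose as Day 0.

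**Inputs**
- End of the on-treatment period and TEAE window: Day 30 (Protocol 8.5.3.1; SAP 15.2), ignoring the earlier cut at new anticancer therapy.
- Permitted visit days: 30 - 5 = 25 to 30 + 5 = 35, which is 35 - 25 + 1 = 11 days (Protocol Table 1-1 and 7.1.4.1).
- End of full AE collection: the day of the actual visit (Protocol 7.1.4.1 and 7.4.1.3).

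**Rules applied to visit day v**
- Laboratory and ECOG results miss the worst-value tables if v > 30.
- TEAE-window days without full AE collection = 30 - v, if v < 30.

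| Visit day | In worst-grade and ECOG-shift tables? | TEAE-window days without full AE collection |
|---|---|---|
| 25 | yes | 5 |
| 26 | yes | 4 |
| 27 | yes | 3 |
| 28 | yes | 2 |
| 29 | yes | 1 |
| 30 | yes | 0 |
| 31 to 35 | no | 0 |

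Five of the 11 days lose the laboratory and ECOG results. A different five lose 1 to 5 days of AE collection, with mean (5 + 4 + 3 + 2 + 1)/5 = 3 days. Only a visit on Day 30 satisfies both rules.

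**Share of subjects.** The documents give no visit-day distribution, so any share is an assumption. If every visit fell on Day 30, both shares would be 0%. If visits were spread evenly, each would be 5/11 = 45%. If every visit fell on Days 31-35, the laboratory and ECOG share would be 100% and the AE share 0%; if every visit fell on Days 25-29, the reverse.

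**Weight of one value.** With all subjects in the denominator, one omitted worst value changes a cohort proportion by 1/6 = 17 percentage points (6 subjects) or 1/3 = 33 points (3 subjects).

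**Can another rule recover the lost data?** The readable SAP has no visit-windowing rule that would assign a Day 31-35 visit to the on-treatment period. The 90-day call (Protocol 7.1.4.2) asks only about SAEs and treatment-related nonserious AEs, so it does not recover unrelated nonserious events.

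**After the fix.** With the laboratory and ECOG window running to Day 35, 0 of 11 visit days miss the tables. With all AEs collected to the later of the visit and Day 30, 0 of 11 leave a gap.

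**The case against.** The strongest reply is that little is lost and most of it is visible elsewhere. Much of that stands, and it rules out several stronger readings.

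- A reader might infer that the 30-day visit is the only post-treatment look. It is not. Table 1-1 schedules hematology, full chemistry, vital signs and ECOG at the End-of-Treatment Visit too, within 7 days of the decision to stop. With dosing every 2 weeks and a decision by the next planned dose, that visit falls by about Day 14 + 7 = 21, inside the window. The 30-day visit is the last scheduled look.
- A reader might infer that late Grade 3 values disappear. They do not. The SAP 15.3 listings of clinically significant hematology and biochemistry values are defined by grade alone, and the by-visit summaries include safety follow-up. What is missing is their count in the worst-grade and shift tables.
- A reader might extend the problem to vital signs and ECG. The vital-sign change categories in SAP 15.4 run from the start of treatment with no on-treatment limit, and no ECG is scheduled at the 30-day visit.
- A reader might infer that late AEs in general depend on visit day. TEAE status follows onset date, and SAEs and treatment-related nonserious AEs are collected to the 90-day call whatever the visit day. AEs starting after the on-treatment period, if collected, are flagged and listed separately.

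It can also be said that on study was meant as on treatment, since Protocol 8.5.3.1 defines the on-treatment period a little earlier. The laboratory sentence does not use that term, however, and sets no end point, so the two texts still need reconciling.

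None of this puts a Day 31-35 result into the worst-value tables or recovers an uncollected event.

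**Conclusion.** The mismatch is real and limited. Results from compliant Day 31-35 visits are left out of the worst-grade, grade-shift, normal-range-shift and ECOG-shift tables. For laboratory grades this departs from the protocol without being declared; the protocol sets no matching rule for ECOG. The graded parameters affected are those in hematology and core chemistry, because full chemistry is not scheduled at this visit. On the AE side, the loss is confined to unrelated nonserious events starting in at most 5 days after an early visit.

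Five of 11 permitted days produce each problem. That count follows from the text alone. The 45% share does not: it needs an even spread of visits and should not be read as an expected rate.

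The tables are descriptive. Nothing here touches DLTs, PK, antidrug antibodies or dose-escalation decisions, and the treatment-related AE endpoint is unaffected. The point is worth correcting because the cohorts are small and the change is cheap.

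**What to change.** **SAP 15.3 and 15.5.2:** include results of the scheduled 30-day Safety Follow-up Visit on any permitted day, that is to last dose + 35 days, still cut at the start of new anticancer drug therapy. This brings the laboratory tables closer to Protocol 8.5.3.1. The cut at new therapy is still narrower than a literal reading of the protocol sentence, so record it in SAP Section 7. SAP 15.4 and 15.5.1 need no change.

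**Protocol 7.1.4.1 and 7.4.1.3:** collect all AEs through the later of the visit and last dose + 30 days, for example by making the visit window 30 (+5) days. Asking about the missing days at the 90-day call is weaker, because it relies on recall of minor events about 90 - 30 = 60 days later.

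**Cost:** SAP wording, plus one protocol line or an eCRF completion instruction. The laboratory and ECOG window becomes up to 5 days longer than the TEAE window, which a table footnote should state, and a few more events will be counted.
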